5.2 Primary Efficacy Endpoint

The primary endpoint used to assess the efficacy objective will be the mean change in Hb between Baseline (mean pretreatment Hb) and the primary evaluation period (mean Hb from Weeks 24 to 36).

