- Temporary discontinuation of study medication.
- Repeat testing of ALT, AST, ALP, and total bilirubin, should be completed within 48 to 72 hours to confirm the abnormalities and to determine trend.
- Study medication should not be resumed until monitoring indicates abnormalities have resolved, are stable, or are not rapidly increasing.

Details on the management of subjects with other ALT and AST abnormalities are further described in [Section 9.4, Study Medication Stopping Rules](#).

Worsening of Anemia – In this study, it is possible that some subjects may experience a worsening of anemia. As the primary endpoint of this study assesses Hb response, worsening of anemia is captured as part of this efficacy parameter. Worsening of anemia should not be considered an AE unless the worsening of anemia is associated with a cause *other than* the subject's CKD.

Transplantation – During this long-term study, it is anticipated that some subjects may receive a kidney transplant. These events will not be recorded as AEs. Subjects will discontinue study medication for receipt of a kidney, other solid organ, hematopoietic stem cell or bone marrow transplant and should continue with the Schedule of Activities and safety assessments as described in [Section 7.5.5.2, Permanent Discontinuation of Study Medication](#).

Malignancy – During this long-term study, some subjects may develop a newly diagnosed malignancy or a recurrence of a malignancy. At the discretion of the Investigator, these subjects may continue study medication (vadadustat or darbepoetin alfa). For reporting of adverse events of malignancy, see Section 10.1.2 Serious Adverse Events.

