10.1.2 Serious Adverse Events

Each AE is to be classified by the Investigator as SERIOUS or NONSERIOUS. An AE that meets 1 or more of the following criteria/outcomes is classified as serious:

- Death.
- Life-threatening (see paragraph below on life-threatening).
- In-patient hospitalization or prolongation of existing hospitalization (see paragraph below on hospitalization).
- Persistent or significant disability/incapacity (see paragraph below on disability).
- Congenital anomaly/birth defect.
- Is considered a medically important event not meeting the above criteria, but which may jeopardize a subject, or may require medical or surgical intervention to prevent one of the criteria listed in this definition.

In addition to the above criteria for classifying AEs as serious, the following situation will also be classified as serious for purposes of this study:

- Malignancies – Newly diagnosed malignancies or a recurrence of a malignancy should be reported as an SAE with the seriousness criterion “medically important” if no other seriousness criteria are met. If a subject develops basal cell carcinoma of skin, squamous cell carcinoma of skin, or cervical carcinoma in situ during the study, or has worsening of these events from Baseline, the Investigator will determine if the event is reported as an AE or SAE.
- Designated Medical Events - The sponsor maintains a list of designated medical events (DME) that they will always classify as serious adverse events. If an event on the DME list is reported as an AE additional information on the event (e.g. investigator confirmation of seriousness, causality) will be requested from the Investigator.

Serious also includes any other event that the Investigator or Sponsor judges to be serious. If there is any doubt whether the information constitutes an AE or SAE, the information is to be treated as an SAE.

The Sponsor has a list of events that they classify as “always serious” events. If an AE is reported that is considered to be an event per this classification as “always serious”, additional information on the event may be requested.

Life-threatening – Any event in which the subject was at risk of death at the time of the event; ‘life-threatening’ does not refer to an event which hypothetically might have caused death if it were more severe.

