11.1.1 Sample Size for the Primary Efficacy Endpoint

The primary efficacy endpoint is defined as the mean change from Baseline in Hb (mean pretreatment Hb) to the average Hb over the primary evaluation period (mean Hb from Weeks 24 to 36, inclusive).

The primary efficacy objective of this study is to show that vadadustat is noninferior to darbepoetin alfa within the noninferiority margin. Noninferiority will be established based on a margin of -0.75 g/dL (for vadadustat minus darbepoetin alfa).

For the primary efficacy analysis in this study, it is assumed that the mean change from Baseline in Hb for vadadustat will be the same as for darbepoetin alfa, and the common standard deviation for the mean change from Baseline is assumed to be 1.5 g/dL. Noninferiority will be established based on a 2-sided 95% confidence interval (CI) for the difference between the vadadustat group and darbepoetin alfa and using a noninferiority margin of -0.75g/dL. With these assumptions and approximately 150 subjects per treatment group for the primary efficacy analysis, the noninferiority assessment will have >90% power.

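### Worsening CKD anemia is exempt from AE reporting with no exception for serious cases, so admissions attributed to it can be left out of the AE and SAE tables

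*Protocol*

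**What the plan says.** Section 10.1.1 (Worsening of Anemia) states that "Worsening of anemia should not be considered an AE unless the worsening of anemia is associated with a cause" other than the subject's CKD. Its reason is: "As the primary endpoint of this study assesses Hb response, worsening of anemia is captured as part of this efficacy parameter". It does not mention hospitalization or any other seriousness criterion.

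Section 10.1.2 defines seriousness by this sentence: "An AE that meets 1 or more of the following criteria/outcomes is classified as serious". One criterion is "In-patient hospitalization or prolongation of existing hospitalization". It then adds a catch-all: "Serious also includes any other event that the Investigator or Sponsor judges to be serious". Doubt between AE and SAE is to be resolved as SAE.

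Section 5.2 defines the primary endpoint as the "mean change in Hb between Baseline (mean pretreatment Hb) and the primary evaluation period (mean Hb from Weeks 24 to 36"). Under 11.6.1.1 the primary analysis keeps Hb measured after rescue therapy and after early discontinuation of study medication.

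Section 5.4 lists Hospitalization, Hb below 8.0 g/dL, and AEs and SAEs as separate safety endpoints.

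**The concern.** The trial asks whether vadadustat treats anemia no worse than darbepoetin alfa. The most direct clinical harm of failing at that is anemia bad enough to put a subject in hospital or threaten life. If such an episode is not an AE, it does not reach the AE and SAE summaries of Section 11.7.2 by the normal route. The SAE comparison is then incomplete for the harm most closely tied to lack of efficacy.

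The exemption would be easier to accept if its stated reason held. A mean laboratory value over one window is a different thing from a record of serious events over the whole follow-up.

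The open-label design adds to the problem. The person deciding whether an episode was due to CKD or to something else, and whether to report it as serious anyway, knows the treatment.

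**Working it through.** No figure in the protocol is in dispute, so most of the check is textual.

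**1. From not an AE to not an SAE.** Section 10.1.1 removes worsening CKD anemia from AEs without qualification. Section 10.1.2 applies its seriousness criteria to AEs. Read together, an admission for worsening CKD anemia meets a criterion but is not the kind of event to which the criteria apply. By contrast, 10.1.2 gives explicit seriousness rules for malignancies.

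**2. Other passages point the other way.**
- The pre-existing conditions paragraph of 10.1.1 makes a condition reportable when it worsens.
- The abnormal test findings paragraph of 10.1.1 makes an abnormal laboratory value that needs treatment an AE.
- Section 10.3.5 offers worsening of the treated condition as a cause for a reported event.
- The medical diagnoses paragraph of 10.1.1 has sites report a known diagnosis in place of its symptoms. Dyspnea or chest pain explained by CKD anemia may therefore drop out along with the diagnosis.

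**3. What the primary endpoint covers.** Section 9 schedules 16 post-baseline visits in Year 1 and 12 more to Week 208, so 28 in all. Weeks 24, 28, 32 and 36 are the window.
- Visits: 4/16 = 25% of Year 1, and 4/28 = 14% of the full schedule.
- Time: (36 − 24)/208 = 12/208 = 5.8%.

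**4. How far worsening moves the primary result.** From 11.1.1: SD 1.5 g/dL, 150 per arm, margin −0.75 g/dL, two-sided 95% CI.
- SE = 1.5 × √(2/150) = 0.173.
- Power with no true difference = Φ(0.75/0.173 − 1.96) = 0.991, consistent with the stated power above 90%.

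For illustration, assume an excess of 10% of vadadustat subjects with a 2 g/dL fall. Shift in the treatment difference = −(excess share × fall × affected visits/4). Probability of concluding noninferiority = Φ((0.75 − |shift|)/SE − 1.96).

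| Worsening | Shift (g/dL) | P(noninferiority) |
|---|---|---|
| Outside Weeks 24–36, or fully corrected before the window | 0 | 0.991 |
| At one of the four visits | −0.10 × 2 × 1/4 = −0.05 | 0.981 |
| At all four visits | −0.10 × 2 × 4/4 = −0.20 | 0.888 |

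Over an assumed excess of 5–15%, falls of 1–3 g/dL and 0–4 affected visits, the shift runs from 0 to −0.45 g/dL and the probability from 0.991 to 0.410. Sustained worsening inside the window does register. Transient, rescued or later worsening hardly does. In no case does the endpoint record that an episode was serious.

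**5. Is Hospitalization collected independently?** Appendix A has no row for it. The visible routes are the AE assessment and the MACE questionnaire. If the endpoint draws on AE records, the exemption reaches it too.

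**The case against.** The strongest reply is that the protocol captures anemia failure by dedicated means:
- Transfusions and ESA rescue are collected at every scheduled post-baseline visit, at EOT and at Follow-up (9.3.5, 9.3.7 to 9.3.10).
- The reason for a transfusion goes on the CRF, and worsening CKD anemia is one of the examples in 8.4.7.1. Reasons for ESA use are recorded as well (8.4.7.2, 8.5.2).
- Central-laboratory CBC continues through the study, and Hb below 8.0 g/dL is a safety endpoint.
- Lack of efficacy is a recorded reason for stopping study medication (7.5.5).
- Deaths, MI, stroke, thromboembolic events and heart-failure admissions are reported for adjudication (10.3.4).
- Section 11.6.1.2 plans a sensitivity analysis that imputes rescue-affected Hb.
- In an open-label trial, judging anemia by objective central Hb rather than by investigator opinion is defensible, and the exemption applies to both arms.

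All of that stands. It rules out two inferences that a reader might draw. One is that an anemia admission can never become an SAE: the catch-all in 10.1.2 leaves a route open. The other is that the harm vanishes from the trial: most of its laboratory and treatment traces remain.

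The reply does not supply the missing piece. Low Hb, transfusion and rescue show that anemia occurred or was treated, not that it was serious. The catch-all is discretionary and runs against an explicit instruction that the event is not an AE, so it is not a reliable safeguard.

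**Conclusion.** The gap is real and worth closing. Sections 10.1.1 and 10.1.2 together allow serious episodes attributed to CKD anemia to go unreported as AEs or SAEs, and the reason given for the exemption is only partly true. The exemption also sits in conflict with other paragraphs of 10.1.1 and with 10.3.5. Information on treatment failure is reduced, chiefly in the SAE comparison and possibly in Hospitalization.

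The number of affected admissions cannot be sized from the protocol, which gives no expected rate of anemia admissions. The figures above describe the coverage and sensitivity of the primary endpoint, and the excess shares and Hb falls in them are assumptions. The effect on Hospitalization depends on how that endpoint is derived, which the SAP may settle.

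A reader might also infer a bias in favor of vadadustat. The protocol does not support that, because nothing in it shows which arm would have more such admissions. What follows is narrower: if the arms do differ in serious anemia, the SAE tables may understate the difference.

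**What to change.** In Section 10.1.1, limit the exemption to worsening of CKD anemia that meets none of the seriousness criteria in 10.1.2. State that worsening which does meet one is recorded as an SAE, and that any admission for it counts under Hospitalization. Align the paragraph with the pre-existing conditions and abnormal test findings paragraphs of 10.1.1, with 10.1.2, and with the cause list in 10.3.5.

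The cost is one sentence, the matching edits and a memo to sites. The downside is somewhat more SAE forms. Treatment, the primary endpoint and the sample size are unchanged.

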10.1.2 Serious Adverse Events

Each AE is to be classified by the Investigator as SERIOUS or NONSERIOUS. An AE that meets 1 or more of the following criteria/outcomes is classified as serious:

- Death.
- Life-threatening (see paragraph below on life-threatening).
- In-patient hospitalization or prolongation of existing hospitalization (see paragraph below on hospitalization).
- Persistent or significant disability/incapacity (see paragraph below on disability).
- Congenital anomaly/birth defect.
- Is considered a medically important event not meeting the above criteria, but which may jeopardize a subject, or may require medical or surgical intervention to prevent one of the criteria listed in this definition.

In addition to the above criteria for classifying AEs as serious, the following situation will also be classified as serious for purposes of this study:

- Malignancies – Newly diagnosed malignancies or a recurrence of a malignancy should be reported as an SAE with the seriousness criterion “medically important” if no other seriousness criteria are met. If a subject develops basal cell carcinoma of skin, squamous cell carcinoma of skin, or cervical carcinoma in situ during the study, or has worsening of these events from Baseline, the Investigator will determine if the event is reported as an AE or SAE.
- Designated Medical Events - The sponsor maintains a list of designated medical events (DME) that they will always classify as serious adverse events. If an event on the DME list is reported as an AE additional information on the event (e.g. investigator confirmation of seriousness, causality) will be requested from the Investigator.

Serious also includes any other event that the Investigator or Sponsor judges to be serious. If there is any doubt whether the information constitutes an AE or SAE, the information is to be treated as an SAE.

The Sponsor has a list of events that they classify as “always serious” events. If an AE is reported that is considered to be an event per this classification as “always serious”, additional information on the event may be requested.

Life-threatening – Any event in which the subject was at risk of death at the time of the event; ‘life-threatening’ does not refer to an event which hypothetically might have caused death if it were more severe.

Hospitalization – Hospitalization is defined as an overnight admission with observation of a minimum of 24 hours. A hospitalization planned before the start of the study for a pre-existing condition that has not worsened during the AE reporting period does not constitute an SAE unless an untoward event occurs related to the procedure.

Disability – Defined as a substantial disruption in a person’s ability to conduct normal life functions.

10.2 Eliciting Adverse Event Information

The Investigator is to report all directly observed AEs and all AEs spontaneously reported by the study subject. In addition, each study subject will be questioned about AEs at each visit following the initiation of treatment.

10.3 Reporting

Each AE is to be classified by the Investigator as SERIOUS or NONSERIOUS.

All AEs that occur in study subjects during the AE reporting period specified in this protocol must be reported, whether or not the event is considered related to study medication (vadadustat or darbepoetin alfa).

10.3.1 Reporting Period

The AE reporting period for this study begins from time of randomization through global study completion.

In addition, any AE that occurs subsequent to the AE reporting period that the Investigator assesses as related to the study medication should also be reported as an AE.

10.3.2 Reporting AEs

NONSERIOUS AEs are to be reported on the AE CRFs.

10.3.3 Reporting SAEs

Any SAE, regardless of causal relationship, must be reported to the Sponsor’s Medical Monitor or CRO designee within 24 hours after the Investigator becomes aware of the SAE. Compliance with this time requirement is essential so that the Sponsor may comply with its regulatory obligations.

The initial SAE report should be completed as fully as possible but should contain, at a minimum:

- Subject number/ID, sex, and age/date of birth.
- The date of report.
- Name of the reporter.
- Name of the suspected medicinal product.
- A description of the event, including event term(s), seriousness criteria, and a clinical summary of the event.
- Causality assessment.

Information about all SAEs (either initial or follow-up information) should be collected and recorded in English on the electronic SAE Report Form within the electronic data capture (EDC) system. The Investigator must assess the relationship to each specific component of the study medication. If the event meets serious criteria and it is not possible to access EDC, a paper SAE Report Form should be sent to the CRO via email or fax, or the Investigator will call the CRO SAE hotline within 24 hours of being made aware of the SAE (reference the site manual for contact information). When the EDC system becomes available, the SAE information must be entered within 24 hours of the system becoming available.

The Investigator must report follow-up information relating to an SAE to the Sponsor's Medical Monitor or CRO designee within 24 hours of awareness by updating the electronic CRF with the new information or by submitting a paper SAE Report Form in the event that the EDC is not available. When the EDC system becomes available, the SAE information must be entered within 24 hours. The subject should be observed and monitored carefully until the condition resolves or stabilizes.

All deaths are to be thoroughly investigated and reported. Autopsy reports and death certificates are to be obtained, if possible.

The Sponsor and/or its designee are responsible for reporting SAEs to all applicable regulatory agencies and the central ethics committees within the required timeline.

The Investigators are responsible for submitting required safety information to their local Institutional Review Board (IRB) or Independent Ethics Committee (IEC) per local regulations. This information includes, but is not limited to, any safety alert letter received from the Sponsor and any SAEs occurring at their investigative site.

10.3.4 Reporting Study Endpoints

Investigators will be counseled to report any event that they assess as potentially being a study endpoint requiring adjudication (death, myocardial infarction, stroke, thromboembolic events, and hospitalization for heart failure). All study endpoint events will be submitted in a blinded fashion to the EAC for adjudication. To protect the integrity of the trial, already adjudicated events will not be unblinded or reported to either Health Authorities (HAs) or Investigators as safety reports unless otherwise requested by HAs or Ethics Committees. After study completion, these events will be included in the final analysis which will be unblinded and submitted to HAs with the study report.

10.3.5 Relationship to Study Medication

The causal relationship of the AE to study medication (vadadustat or darbepoetin alfa) will be assessed by both the Investigator and the Sponsor.

The assessment of causal relationship to study medication should be evidence-based, and not based on the premise that all AEs are possibly causally related to study medication until proven otherwise.

Examples of evidence that would suggest a causal relationship between the study medication and the AE include the occurrence of an AE that is uncommon and known to be strongly associated with drug exposure (e.g., angioedema, hepatic injury, Stevens-Johnson Syndrome), or an AE that is uncommon in the population exposed to the drug.

The causal relationship of the AE is assessed using a binary system, and AEs are classified as either 'related' or 'unrelated':

Related: There is 'reasonable possibility' that the drug caused the AE. The AE follows a reasonable temporal sequence from the time of drug administration. There is supportive evidence (facts) to suggest a possible causal relationship, irrespective of the degree of certainty between the observed AE and the drug.

Unrelated: An AE does not follow a reasonable temporal sequence from administration of the product and/or there is no reasonable possibility that the drug caused the AE. This assessment includes situations where the AE is related to other factors such as the subject's clinical state, other therapeutic interventions, or concomitant drugs administered to the subject.

Default assessments using the 'related' category without supportive evidence for a causal relationship to study medication is generally uninformative and does not contribute meaningfully to the development of the safety profile of the drug or to subject protection.

Investigators are encouraged to choose the most plausible cause for the event(s) from the following list: medical history, lack of efficacy/worsening of treated condition, study medication, other treatment (concomitant, or previous), withdrawal of study medication, administration error, protocol-related procedure, others (specify).

10.3.6 Severity

The Investigator will assess each AE as either MILD, MODERATE, or SEVERE using the following guidelines to describe the maximum severity of the AE:

MILD: Does not interfere with subject's usual function.

MODERATE: Interferes to some extent with subject's usual function

SEVERE: Interferes significantly with subject's usual function.

Note that a **severe** AE is not necessarily a **serious** AE. For example, a headache may be severe in intensity, but would not be classified as serious unless it met 1 of the criteria for serious events listed above.

10.3.7 Follow-up of Unresolved Events

All AEs should be followed until they are resolved or the Investigator assesses them as chronic or stable or the subject's participation in the trial ends (ie, until a final report is completed for that subject).

In addition, all SAEs and those nonserious events assessed by the Investigator as related to the study medication should continue to be followed even after the subject's participation in the trial is over. Such events should be followed until they resolve or until the Investigator assesses them as "chronic" or "stable". Resolution of such events is to be documented on the appropriate CRF.

10.4 Exposure In Utero

A pregnancy in a female subject must be confirmed by a positive serum β human chorionic gonadotropin (β -HCG) test.

The study medication should be immediately discontinued once the pregnancy of a female study participant has been confirmed.

If any study participant becomes or is found to be pregnant while receiving a study medication (vadadustat or darbepoetin alfa) or within 30 days of discontinuing the study medication, the pregnancy must be recorded on the Pregnancy Reporting Form/Exposure in Utero Form in EDC within 24 hours of awareness of the pregnancy or the Investigator will call the CRO SAE hotline within 24 hours of being made aware of the pregnancy.

Pregnancy during this time frame of the female partner of a male subject should also be reported.

The Pregnancy Reporting Form/Exposure in Utero Form must be completed with all known information regarding the pregnancy at the time of reporting. Investigative site personnel will update the form with additional information regarding the pregnancy and the outcome of the pregnancy as it becomes available until the outcome of the pregnancy is reported.

The Investigator will follow the subject (or female partner of a male subject) until completion of the pregnancy. If the outcome of the pregnancy meets the criteria for classification as an SAE (ie, spontaneous abortion, stillbirth, neonatal death within 1 month of birth, or congenital anomaly [including that in an aborted fetus]), the Investigator will also follow the procedures for reporting an SAE within 24 hours of awareness. A pregnancy in and of itself is not considered an AE; however, unexpected complications are considered AEs.

Additional information about pregnancy outcomes follows:

- Note that “spontaneous abortion” includes miscarriage and missed abortion.
- All neonatal deaths that occur within 1 month of birth should be reported, without regard to causality, as SAEs. In addition, any infant death after 1 month that the Investigator assesses as related or unrelated to the in utero exposure to the study medication should also be reported.
- In the case of a live birth, the “normality” of the newborn can be assessed at time of birth.
- The “normality” of an aborted fetus can be assessed by gross visual inspection unless there are pre-abortion laboratory findings suggestive of a congenital anomaly.

